1.1 Study Overview

The study ISIS 678354-CS2 is a Phase 2 multicenter, randomized, double-blind, placebo-controlled, dose-ranging study being conducted at approximately 32 sites in the United States and Canada.

Patients ≥ 18 and ≤ 80 years old with elevated plasma triglyceride levels (≥ 200 mg/dL (≥ 2.3 mmol/L) and ≤ 500 mg/dL (≥ 5.7 mmol/L)) and a clinical diagnosis of established CVD, or at high risk for CVD (as defined in the study protocol), will be eligible for enrollment upon meeting the study specific eligibility criteria. Patients will be on standard-of-care preventative therapy for known CVD risk factors as per current guidelines. The study is comprised of the following periods:

- **Screening:** An up to 4 week Screening Period, including an up to 2-week qualification period following an at least 2-week diet stabilization period, where appropriate. Patients on a stable diet known to the investigator and clinically followed at the site may go from Screening to the qualification visit without a 2-week diet stabilization phase.
- **Treatment Period:** Following qualification, up to approximately 100 eligible patients will be randomized in a 1:1:1:1 ratio to one of the 4 dosing cohorts as shown in [Table 1](#), with each cohort having a 4:1 ratio to receive ISIS 678354 or matching volume of placebo, respectively, by SC injection.

Table 1: Study Drug Dosing Information

Cohort	Treatment	Volume to Administer/Dose	# Doses	Total ISIS 678354
A	10 mg ISIS 678354 or placebo (Every 4 weeks)	0.10 mL	≤ 13	≤ 130 mg
B	50 mg ISIS 678354 or placebo (Every 4 weeks)	0.50 mL	≤ 13	≤ 650 mg
C	15 mg ISIS 678354 or placebo (Every 2 weeks)	0.15 mL	≤ 26	≤ 390 mg
D	10 mg ISIS 678354 or placebo (Every week)	0.10 mL	≤ 52	≤ 520 mg

The minimum treatment duration for all patients is 6 months and the maximum is 12 months. The treatment portion of the study will be complete when the last patient reaches 6 months of exposure, at which time patients still receiving Study Drug (ISIS 678354 or placebo) will transition to the Post-Treatment Follow-up Period.

The End of Treatment (EoT) visit for all patients should be scheduled no later than the EoT visit of the last patient to reach 6 months of exposure. The EoT visit should be scheduled to occur at one dosing interval post last dose of Study Drug: one week post last dose for weekly treatment (Cohort D), 2 weeks post last dose for every 2-week treatment (Cohort C), and 4 weeks post last dose for every 4-week treatment (Cohorts A-B). For any patient whose EoT visit would occur later than the EoT visit for the last patient to reach 6 months of exposure, the primary endpoint visit (Week 25 or Week 27 depending on Cohort) will count as the EoT visit.

- **Post-Treatment Follow-up Period:** After the EoT visit has been completed, patients will enter the 13-week post-treatment follow-up period and will return to the Study Center for 3 follow-up visits at 4, 8, and 13 weeks post EoT visit.

1.2 *Objectives*

1.2.1 *Primary Objective*

To evaluate the safety, including tolerability, of ISIS 678354 and to assess the efficacy of different doses and dosing regimens of ISIS 678354 for reduction of serum triglyceride levels in patients with hypertriglyceridemia and established CVD or at a high risk for CVD.

1.2.2 *Secondary Objectives*

To evaluate the efficacy of ISIS 678354 on serum levels of apolipoprotein C-3 (apoC-III), total cholesterol (TC), low density lipoprotein cholesterol (LDL-C), high density lipoprotein cholesterol (HDL-C), non-high density lipoprotein cholesterol (non-HDL-C), very low density lipoprotein cholesterol (VLDL-C), apolipoprotein B100 (apoB) and apolipoprotein A-1 (apoA-I).

To evaluate pharmacokinetics (PK) of ISIS 678354 across different doses and dose regimens in patients with hypertriglyceridemia and established CVD or at a high risk for CVD.

1.2.3 *Exploratory Objectives*

To evaluate the efficacy of ISIS 678354 on serum levels of lipoprotein(a) [Lp(a)], remnant cholesterol, and angiopoietin-like 3 (ANGPTL3).

1.3 *Hypotheses*

The study hypothesis is that ISIS 678354 can significantly reduce the serum triglyceride levels and is well-tolerated for patients with established CVD or at a high risk for CVD.

1.4 *Endpoints*

The primary analysis time point (PAT) is at Week 25 for patients who received every 4-week dosing (Cohorts A and B) and at Week 27 for patients who received weekly or biweekly dosing (Cohorts C

and D). For patients continuing treatment beyond the PAT additional supportive efficacy and safety analyses will be repeated at the completion of Study Drug treatment. A final analysis will be conducted after all patients have completed their post-treatment follow-up visits.

1.4.1 Primary Efficacy Endpoint

Percent change in fasting triglyceride level from Baseline to the PAT.

1.4.2 Secondary Efficacy Endpoints

The secondary endpoints are the following at the PAT:

- Percent change from Baseline in apoC-III, TC, LDL-C, HDL-C, non-HDL-C, VLDL-C, apoB, and apoA-I
- Proportion of patients who achieve serum triglycerides ≤ 150 mg/dL (≤ 1.7 mmol/L)
- Proportion of patients who achieve triglycerides ≤ 100 mg/dL (≤ 1.13 mmol/L)

1.4.3 Exploratory Endpoints

Percent change in Lp(a), remnant cholesterol, and ANGPTL3 from Baseline to the PAT.

Remnant cholesterol will be calculated using the following formula:

$$\text{Remnant cholesterol} = \text{TC} - (\text{LDL-C} + \text{HDL-C})$$

1.4.4 Safety Endpoints

The safety analysis will be performed using the following parameters:

- Adverse events (AEs)
- Vital signs and weight
- Physical examinations
- Clinical laboratory tests (serum chemistry, hematology, coagulation, urinalysis)
- Proportion of patients with platelet drop by severity, including platelet drop below lower limit of normal (LLN), platelet drop greater than 30% from baseline, or any platelet drop meeting stopping rules.
- Proportion of patients with liver adverse events by severity, number of patients meeting liver stopping rules, and change in liver function tests by severity.
- Proportion of patients with renal adverse events by severity, number of patients meeting renal stopping rules, and change in renal function tests by severity.
- Electrocardiograms (ECGs) (including serial ECGs in a subgroup of patients undergoing serial PK sampling)
- Use of concomitant medications

2 PROCEDURES

The study for an individual patient will generally consist of the following periods (see also Section 1.1):

- A Screening Period (up to 4 weeks), including an up to 2-week qualification period following an at least 2-week diet stabilization phase, where appropriate
- A Treatment Period (up to 52 weeks) during which Study Drug will be administered per assigned cohort by SC injection
- A Post-treatment Follow-up Period (13 weeks)

2.1 General Overview of Procedures

2.1.1 Screening Period

Written informed consent for the study will be obtained prior to the performance of any study-related procedures including screening procedures. An up to 4-week period is provided for completing screening assessments and determining patient eligibility for the study. Abnormal screening results may be re-tested once for determination of patient eligibility after consultation with the Sponsor Medical Monitor. Patients may be re-screened 1 time in order to determine eligibility. During the screening period, patients will undergo a medical history and physical examination including vital signs, 12-lead ECG and have blood and urine samples taken for clinical laboratory testing. Patients will be screened for Human Immunodeficiency Virus (HIV), hepatitis B, and hepatitis C.

2.1.2 Treatment Period

Patients will receive the Study Drug (ISIS 678354 or placebo) administered by SC injection as shown in Table 1. Collection and measurement of vital signs, physical examination results, ECGs, clinical laboratory parameters, ISIS 678354 plasma concentrations, anti-drug antibody (ADA) and biomarker samples, AEs and concomitant medication/procedure information will be performed according to the Schedule of Procedures in Protocol Appendix A. A list of laboratory analytes required for the study is contained in Protocol Appendix B. Protocol Appendix C details the PK sampling schedules. Within each cohort, a subgroup of approximately 10 patients, who will consent to extensive PK sampling, will undergo additional PK sampling, in what is referred to as the PK Subgroup in this study. Patients in this subgroup will have additional PK sampling time points, additional ECG assessments, and additional clinic visits during the treatment period according to the PK Sampling Schedule in Protocol Appendix C.

2.1.3 Post-Treatment Follow-Up Period

Following the end of the treatment period, patients will enter a 13-week Post-Treatment Follow-up Period and return to the Study Center for 3 outpatient visits outlined in the Schedule of Procedures in Protocol Appendix A and C.

2.2 Randomization and Treatment Allocation

Patients will be randomized after all screening and qualification assessments have been completed and after the Investigator has verified, they are eligible per criteria in the protocol sections 5.1 and 5.2. No patient may begin treatment prior to randomization and assignment of a unique patient identification number.

Using an Interactive Web-Response System (IWRS), eligible patients will be randomized in a 1:1:1:1 ratio to 1 of the 4 parallel-dose cohorts (Cohorts A, B, C or D). Within each dose cohort, patients will be randomized in a 4:1 ratio to receive ISIS 678354 or matching volume of placebo, respectively.

A permuted block schedule will be used. The randomization schedule will be generated and held by an independent vendor. Patients who withdraw from the study will not be replaced. The study is planned to randomize approximately 100 patients.

2.3 Conduct

The study will be conducted in accordance with current Good Clinical Practice (GCP) and International Conference on Harmonization (ICH) guidelines, the World Medical Association Declaration of Helsinki guidelines, the Food and Drug Agency (FDA) Code of Federal Regulations, and all other local regulatory requirements.

2.4 Data Monitoring

In order to ensure maintenance of the study blind, the results of efficacy parameters consisting of lipid panel results including apoA-I, apoB, apoC-III, TC, LDL-C, HDL-C, non-HDL-C, VLDL-C, triglycerides, ANGPTL3 and Lp(a) will be blinded to the Akcea study team, Clinical Research Organization (CRO) study team, Investigators, Study Center personnel and patients until after database lock for EoT. After Sponsor's unblinding post completion of treatment period, blinded study personnel will continue to oversee the study until all patients completed the study.

2.4.1 Safety Data Monitoring

Safety information will be collected, reviewed, and evaluated by Akcea (or designee) in accordance with the Safety Management Plan throughout the conduct of the clinical trial.

In addition to the standard monitoring of clinical safety parameters, there are individual monitoring rules for the selected parameters related to renal, liver function, platelet count, bleeding events, constitutional symptoms, and glycemic control, described in the Protocol Section 8.5. The stopping rules and adjustment of dose are specified in protocol Sections 8.6 and 8.7

Akcea (or designee) is responsible for regulatory submissions and reporting to the Investigators of suspected unexpected serious adverse reactions (SUSARs) per ICH guidelines. Processing of serious adverse events (SAEs) is delegated to a third-party vendor although Akcea remains accountable for this activity and process. AEs and SAEs are reviewed according to standard operating procedures.

The Study Medical Monitor will review all AEs and SAEs on an ongoing basis throughout the study. Monitoring of AEs are outlined in the Protocol section 9.4

2.4.2 Data Safety Monitoring Board

An independent Data and Safety Monitoring Board (DSMB) will be assembled to review safety, tolerability and efficacy (as needed) data collected on ISIS 678354 during this study. Based on its ongoing assessment of the safety and tolerability of ISIS 678354, the DSMB will provide recommendations to Akcea for modifying, stopping or continuing the study as planned. Details on the safety assessments, frequency of review, meeting schedules and controlled access to unblinded data are outlined in the DSMB Charter.

2.5 Data Management

2.5.1 Case Report Form (CRF) Data

Bioclinica® is responsible for creating the Electronic Data Capture (EDC) data entry screens, database and edit checks using definitions developed by the Sponsor (or designee).

Trennic Data Services, a data management vendor contracted by Akcea, is responsible for creating CRF Completion Guidelines (CCGs) and will oversee the development of the Electronic Data Capture (EDC) system by the EDC hosting vendor. Akcea (or designee) is responsible for the review, querying, and locking of the database.

2.5.2 Laboratory Data

Trennic Data Services is responsible for the format of the laboratory electronic data transfers and the transfer schedule. Akcea is responsible for the review of the clinical laboratory data. Central lab data managed by Medpace Reference Laboratories (MRL) are not stored in the EDC system but will be transferred to Trennic Data Services. Investigator sites have access to this data via lab reports sent directly from MRL.

2.5.3 Pharmacokinetics and Anti-drug Antibody Data

PPD and Charles River Laboratories are responsible for the production of PK and anti-drug antibody (ADA) data respectively. Akcea is responsible for the review of the data. This process involves reviewing the patient and visit identifiers with the clinical data collected in the EDC system. The PK and ADA results are not stored in the EDC system but will be transferred to Akcea Therapeutics, Inc. or designee as external data.

2.5.4 Other Data

Almac manages and produces randomization code. The User Acceptance Testing (UAT) data will be delivered prior to the database lock for pre-programming. The actual data will be delivered after database lock. Data will not be stored in the EDC system, but will be transferred to Parexel as external data.

3 ANALYSIS PLANS

3.1 Statistical Design Summary

This is a multi-center, randomized, double blind, placebo-controlled study.

The study hypotheses will be formally evaluated at the planned EoT analysis on data obtained through the data cut-off date, defined as the date of the last EoT visit. The database will be queried, and data cleaning performed on all data, with database interim lock of all data, at which point the treatment code is unblinded and the EoT analysis is performed.

The primary analysis model will be an Analysis of Covariance (ANCOVA) model for percent change from baseline to the PAT in fasting triglycerides. Missing data will be imputed by a multiple imputation method as the primary analysis and will be supported by various sensitivity analyses.

The treatment groups proposed in this analysis are defined as follows:

- ISIS 678354 10 mg every 4 weeks (Q4W)
- ISIS 678354 50 mg every 4 weeks (Q4W)
- ISIS 678354 15 mg every 2 weeks (Q2W)
- ISIS 678354 10 mg every week (QW)
- Pooled Placebo, defined as the combined group of placebo patients from the 4 randomized cohorts

A final analysis will be performed after all data from the 13-week post treatment follow-up period are collected and locked.

3.2 General Overview of Analyses

This analysis plan describes the reporting of data at 1) all patients completed the primary analysis time point 2) all patients completed the study.

3.2.1 General Conventions

All reporting will be performed in SAS version 9.3 or higher.

All eCRF data and lab data transfers, as well as any outcomes derived from the data, will be provided in the patient data listings. Patient data listings will be presented for all patients enrolled into the study, and will be sorted by treatment group, patient ID, visit, and time point (where appropriate).

3.2.2 Reporting Conventions

Efficacy results will be summarized under the treatment to which patients were randomized. Safety and PK results will be summarized under the treatment which patients actually received. Should there be any cases after unblinding in which a patient received treatment other than what the patient was

randomized to, such cases will be discussed in the study report and noted in footnotes where applicable.

All tables will present the population frequencies in each treatment group and/or subgroup (where appropriate) and will indicate the number of patients with non-missing data and the denominators for percentages.

Descriptive summary statistics including n, mean, median, standard error, standard deviation SD, interquartile range (25th percentile, 75th percentile), range (minimum, maximum), mean 95% confidence interval (CI) for continuous variables, and counts and percentages for categorical variables, will be used to summarize data by treatment group. Summaries of PK concentrations and parameters will also include coefficient of variation (CV%), geometric mean, and geometric CV%. Where appropriate, p-values will be reported. All statistical tests will be conducted using 2-sided tests with 5% Type I error rates unless otherwise stated.

Except summaries for PK parameters, precision for displays will use the following conventions. Means, percentiles (e.g., median, 25th and 75th percentile), least squares means, difference in least squares means will be displayed to one more decimal place than measured values. Standard deviations and standard errors will be displayed to two more decimal places than measured values. The minimum, maximum and confidence intervals will be displayed using the same number of decimal places as the recorded values. All raw values presented in listings will be displayed to the measured precision. Percentages will be displayed to one decimal place. For PK concentrations and parameters, mean, standard deviation, standard error, geometric mean, median, minimum, and maximum values will be presented to 3 significant digits and CV% and geometric CV% will be presented to one decimal place. p-value will be displayed to 4 decimal places. p-value less than 0.0001 will be presented as “<0.0001”. p-value greater than 0.9999 will be displayed as “>0.9999”. Confidence intervals will be presented using a comma separator rather than a dash.

Age will be presented in years. Weight will be presented in kg. Height will be presented in cm. Temperature will be presented in °C. Laboratory listings will be presented using original unit. Summary tables of lab results will be based on original unit. For multiple original units within the parameters, the results will be converted to the majority of units as reported. Lab shift tables and abnormalities tables will be based on mock shell displays.

The lab data will be reported using central lab and/or local lab depending on the type of outputs or values. [Table 2](#) and [Table 3](#) outline which data source, lab unit and visits should be used for the specific outputs and values.

Table 2: Summary of Lab Data Source per Type of outputs

	Type of Outputs	Data source	Unit	Visits
--	-----------------	-------------	------	--------

Listings	Listings of lab data	Central and local lab in separate listings	Original Unit	SCH + USCH visits
Tables, Figures	All efficacy endpoints (primary, secondary, exploratory)	Central lab	Original Unit	analysis SCH + USCH within visit window
	Descriptive summary of platelet count data	Central and local lab, separate tables and figures	Original Unit (cells/mm ³)	nominal SCH visits
	Descriptive summary safety lab data other than platelet counts	Central lab	Original Unit	nominal SCH visits
	Safety shift tables	Central and local lab	Per mock shells	nominal SCH + USCH visits
	Abnormalities lab tables	Central and local lab	Per mock shells	nominal SCH + USCH visits

SCH: scheduled; USCH: unscheduled

Table 3: Summary of Lab Data Source per Type of Values

Type of values	Data source	Unit	Visits
Baseline for platelet count	Central and local lab	Original Unit (cells/mm ³)	SCH + USCH visits prior to the first dose of Study Drug
Baseline for other safety labs	Central lab	Original Unit	nominal based on SCH + USCH visits; selected as last non missing prior to first dose of Study Drug
Confirmed lab value	Central and local lab	Per mock shells	nominal SCH + USCH visits

SCH: scheduled; USCH: unscheduled

Efficacy assessments (i.e. lipid panel) will be mapped to an analysis visit per the analysis visit windows as specified in [Appendix A](#) and summarized by analysis visit. The selection rule of analysis visits is specified in [Appendix A](#) as well.

Safety assessments will be summarized by nominal visit as collected in CRF. For summary tables by nominal visit, only scheduled visits will be used. For multiple records at the nominal (scheduled) visit, the average will be used for continuous values, or the worst will be used for categorical values.

For summary tables of platelet counts by nominal visit, scheduled visits from central lab data and separately, from local lab data will be used. For multiple records at the nominal (scheduled) visit, the average will be used for continuous values, or the worst will be used for categorical values.

3.2.2 *Patient Population Analyzed*

The following analysis sets will be used for the analysis of data as described within each analysis set.

Screened Patients are defined as the patients who sign an informed consent form.

Randomized Patients are defined as the patients who receive a randomization assignment.

Full Analysis Set (FAS): All patients who are randomized and received at least 1 dose of Study Drug (ISIS 678354 or placebo). The FAS represents the practically-feasible intent-to-treat (ITT) population as delineated in International Conference on Harmonisation (ICH) Guideline E9. This population will be used for the analysis of efficacy.

Per Protocol Set (PPS): Subset of the FAS who received prior to the Primary Analysis Timepoint at least 5 monthly doses of Study Drug for patients randomized in Cohorts A and B, or at least 11 every 2-week doses for patients randomized in Cohort C, or at least 22 weekly doses for patients randomized in Cohort D, and who have no major protocol deviations that could compromise the interpretation of efficacy. Major deviations will be determined prior to unblinding for statistical analysis. This population will be used for supportive inferences concerning efficacy.

Safety Set (SS): All patients who are randomized and received at least 1 dose of Study Drug. This population will be used for all safety analyses.

PK Population: All patients who are randomized and received at least 1 dose of ISIS 678354, and have at least 1 evaluable concentration result post first dose. This population will be used for analysis of PK data.

PK Subgroup: A subset of PK population who will undergo additional PK sampling after dose administration on Day 1 and Week 21 (Cohorts A and B) / Week 25 (Cohorts C and D) to evaluate the plasma PK parameters of ISIS 678354.

Patients in PK subgroup will also have additional ECGs conducted as indicated in [Table 4](#).

Table 4: Additional PK Sampling and ECG Schedule for PK Subgroup

Cohort	Additional PK Sampling	Additional ECGs
--------	------------------------	-----------------

Cohort A and B	Week 1 (1, 2, 4, 8, 24 hr post-dose), Week 21 (1, 2, 4, 8, 24, 48 hr post-dose), Week 22 (Anytime), Week 23 (Anytime)	Week 1 (1, 2, 4, 8, 24 hr post-dose), Week 21 (1, 2, 4, 8, 24 hr post-dose)
Cohort C	Week 1 (1, 2, 4, 8, 24 hr post-dose), Week 25 (1, 2, 4, 8, 24, 48 hr post-dose), Week 26 (Anytime), Week 27 (pre-dose)	Week 1 (1, 2, 4, 8, 24 hr post-dose), Week 25 (1, 2, 4, 8, 24 hr post-dose)
Cohort D	Week 1 (1, 2, 4, 8, 24 hr post-dose), Week 25 (1, 2, 4, 8, 24, 48 hr post-dose), Week 26 (pre-dose)	Week 1 (1, 2, 4, 8, 24 hr post-dose), Week 25 (1, 2, 4, 8, 24 hr post-dose)

PK-ECG Set: All patients who provide baseline ECG data and at least one post-baseline matched PK before onset of anti-drug antibody and ECG record. This population will be used to analyze the exposure-QTcF relationship. Patients determined to have a pacemaker rhythm will be excluded from the PK-ECG Set.

All primary and secondary efficacy endpoints will be assessed in the FAS and PPS, with the former being the basis for the primary efficacy analysis. All exploratory efficacy endpoints will be assessed in the FAS. All safety assessments will be performed on the SS. PK endpoints will be assessed in the PK Population and PK Subgroup as applicable.

Patients in randomization populations, FAS and PPS will be analyzed in the treatment group to which they were randomized. Patients in SS, PK Population, PK Subgroup, and PK-ECG Set will be analyzed in the group with actual treatment they received.

[REDACTED]

[REDACTED]

[REDACTED]

[REDACTED]

[REDACTED]

[REDACTED]

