3.4.1 Screening

Patient eligibility for the study will be determined within 4 weeks prior to study.

3.4.2 *Treatment*

For each patient, minimum treatment duration is 6 months and a maximum of 52 weeks.

All patients enrolled will be randomized to a minimum of 6 months of treatment in 1 of 4 treatment cohorts. On completion of the 6 months, patients will continue treatment within the same randomized cohort until the last patient reaches 6 months of exposure (for continuing safety assessments), with a maximal exposure period of 12 months. The End of Treatment visits for all patients on treatment will be scheduled no later than the End of Treatment visit of the last patient to complete 6 months of exposure.

The End of Treatment visit should be scheduled one dosing interval post last dose of study drug: one week post last dose for weekly dosing (Cohort D), 2 weeks post last dose for every 2-week dosing (Cohort C), and 4 weeks post last dose for every 4-week dosing (Cohorts A-B). The procedures scheduled for the Week 53/ET visit ([Appendix A](#)) will be performed at the End of Treatment visit. Following the End of Treatment visit patients will then enter a 13-week post-treatment follow-up period.

Eligible patients will report to the Study Center for assessments at specified intervals throughout the 52-week treatment period as detailed in the Schedule of Procedures in [Appendix A](#). During the Treatment, Study Drug (ISIS 678354 or placebo) will be administered by SC injection once-weekly, every 2 weeks, or every 4 weeks, depending on cohort assignment.

3.4.3 *Post-Treatment*

Patients, when completed dosing, will enter the 13-week post-treatment follow-up period and will return to the Study Center for 3 follow-up visits at 4, 8, and 13 weeks post End of Treatment period as per [Appendix A](#) (Follow-up).

The final study visit for each patient will be 13 weeks post End of Treatment period. End of Treatment period is defined as one dosing interval post last dose.

3.5 *End-of-Study*

The End-of-Study is defined as last patient, last visit.

For individual patients, End-of-Study is defined as completion of their last study visit.

3.6 *Data and Safety Monitoring Board*

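### After the primary time point the SAP's lipid windows have three 28-day gaps and no End of Treatment visit, so some End of Treatment lipid values drop out of the supportive efficacy analyses

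*Combined protocol and SAP*

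**What the plan says.** **When treatment ends.** Protocol Section 3.4.2: "For each patient, minimum treatment duration is 6 months and a maximum of 52 weeks". The same section ties the end to the calendar: "The End of Treatment visits for all patients on treatment will be scheduled no later than the End of Treatment visit of the last patient", meaning the last one to reach the 6-month mark. SAP 1.1 fixes the interval from the last dose: "The EoT visit should be scheduled to occur at one dosing interval post last dose of Study Drug", that is 28, 14 or 7 days. For a patient whose EoT would otherwise fall after the last patient's, "the primary endpoint visit (Week 25 or Week 27 depending on Cohort) will count as the EoT visit".

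**What is measured.** Under Protocol Section 3.4.2, "The procedures scheduled for the Week 53/ET visit" are carried out at the EoT visit, whichever study week that is. In the weekly and every-2-week schedule (Protocol Appendix A) the Week 53/ET column includes the lipid panel.

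**What is promised.** Protocol Sections 3.1 and 10.1 and SAP 1.4 say that, for patients treated beyond the primary time point, "additional supportive efficacy and safety analyses will be repeated at the completion of Study Drug treatment".

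**How lipid values reach the tables.** SAP 3.2.2: "Efficacy assessments (i.e. lipid panel) will be mapped to an analysis visit per the analysis visit windows" in SAP Appendix A. Table 2 in that section limits the records used for efficacy tables and figures to "analysis SCH + USCH within visit window". The MMRM (SAP 3.3.3, Sensitivity Analysis 6, and SAP Appendix B) uses the same mapping. Its later visits are Weeks 29, 37, 45 and 53, each included only if at least 10% of the FAS has data there.

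**The concern.** The windows after the primary time point appear to be built around routine lipid visits. EoT visits, and late early-termination visits, follow the dosing grid and the calendar close-out, so they can fall between those windows. If the SAP is programmed exactly as written, whether a continuing patient's last on-treatment triglyceride, apoC-III or apoB value enters a table depends on enrolment date. SAP 3.1 breaks the treatment code at the EoT lock, so a rule for EoT values chosen after that point would be post hoc. What is at stake is the precision and clarity of the supportive efficacy results at completion of treatment.

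**Working it through.** The plan states no figure on this point. The check is a mapping exercise, followed by a calculation that rests on an assumed accrual period.

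**1. Target days.** Day = 7 × (week − 1) + 1. This reproduces the SAP Appendix A targets for Weeks 25, 27, 29, 37, 45 and 53: Days 169, 183, 197, 253, 309 and 365. Weeks 33, 41 and 49 are Days 225, 281 and 337, as in Protocol Appendix A.

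**2. Windows from the primary time point on (SAP Appendix A).**
- Cohorts A/B: 156-183 (primary), 184-211, 240-267, 296-323, 352-379.
- Cohorts C/D: 156-190 (primary), 191-211, then the same three.
- Unmapped in both: 212-239, 268-295 and 324-351, which is 3 × 28 = 84 days. That is 84/196 = 43% of Days 184-379 (A/B) and 84/189 = 44% of Days 191-379 (C/D).

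**3. Possible EoT days after the primary visit, up to Day 365.**
- Every 4 weeks (197, 225, ..., 365): unmapped at 225, 281 and 337, so 3 of 7.
- Every 2 weeks (197, 211, ..., 365): unmapped at 225, 239, 281, 295, 337 and 351, so 6 of 13.
- Weekly (190, 197, ..., 365): unmapped at 218-239, 274-295 and 330-351 in steps of 7, so 12 of 26.

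EoT at the primary visit itself, or at Week 53, is mapped.

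**4. Share of patients affected.** Assumptions: accrual is uniform over R days, nobody drops out, close-out is when the last patient reaches Day 183, and each EoT is on the latest permitted grid day. A patient enrolled u days before the last one then has EoT on the last grid day not after 183 + u, capped at 365. For every-4-week dosing, EoT is Day 225 when 42 ≤ u < 70, Day 281 when 98 ≤ u < 126, and Day 337 when 154 ≤ u < 182. The other two regimens also give 28 days of u per gap. The share is therefore 28 × (gaps reached)/R:
- 3 months (R = 91): 28/91 = 31%
- 6 months (R = 182): 84/182 = 46%
- 9 months (R = 274): 84/274 = 31%
- 12 months (R = 365): 84/365 = 23%
- 18 months (R = 547): 84/547 = 15%

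A simulation across the four cohorts gave the same values. Closing out at Day 169 of the last patient instead changes the 6-month figure to about 40% and leaves the others essentially unchanged. With about 100 patients, the range is roughly 15 to 46 patients.

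**5. What an affected patient keeps.** If the routine Week 29, 37 and 45 panels are on target, the last mapped value is 21 to 42 days before the lost one (218 − 197 = 21; 239 − 197 = 42), and 28 days before it for every-4-week dosing (225 − 197).

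**6. After the fix.** With an EoT analysis visit, no possible EoT day is left without one in any regimen.

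**The case against.** The strongest reply is that completion of treatment says when the analysis is run, not which visit is analysed. SAP 3.1 uses the term EoT analysis in that sense: data up to the last EoT visit, interim lock, unblinding. Every listed efficacy endpoint is defined at the primary time point. On this reading, the by-visit summaries and the MMRM already supply the supportive results. This reading is open, so it goes too far to say that the promised analysis cannot be produced. It does not remove the gap, because those summaries and the MMRM still omit EoT values under the window rule.

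Other points against also stand:
- A reader might infer that the primary result is at risk. It is not: the windows are contiguous through Day 211, and the primary, secondary and exploratory analyses at the primary time point are unaffected.
- A reader might infer that evidence on 6-to-12-month durability, or on every-4-week against weekly dosing, is undermined. No objective, endpoint or dose-selection criterion concerns late durability, and Protocol Section 3.4.2 gives further safety observation as the reason for treating past 6 months. Safety data are summarised by nominal visit, so the windows do not touch them.
- The shrinking group at later weeks comes from enrolment dates and the common close-out, not from the windows. No bias has been shown.
- The 43-44% of unmapped days is not a share of lost data. As far as the weekly and every-2-week schedule can be read, routine panels are not placed in the gaps. The every-4-week lipid row is not legible in the text I worked from.

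**Conclusion.** The point holds in a limited form. Followed exactly, the SAP leaves EoT lipid values from Days 212-239, 268-295 and 324-351 out of the efficacy tables, figures and MMRM, and it defines no EoT analysis visit. They remain in the listings, and an affected patient usually keeps a mapped value from about four weeks earlier. The consequence is lost precision in the supportive efficacy analysis, together with doubt about what that analysis is.

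The gaps and the counts of unmapped EoT days follow directly from the documents. The 15% to 46% of patients does not: it rests on assumed uniform accrual over 3 to 18 months, no dropout and EoT on the latest permitted day. Part of the SAP just before its Section 3.2.4 is blacked out. A rule hidden there would still have to be reconciled with the readable window rule and Appendix A.

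**What to change.** Before the EoT lock, make two changes to the SAP:

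1. Add an End of Treatment analysis visit to SAP Appendix A: the last fasting post-baseline lipid value no later than last dose plus one dosing interval plus the 3-day visit window.
2. State that the supportive efficacy analysis at completion of treatment is the log-ratio ANCOVA against pooled placebo at that visit, shown with time on treatment.

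Contiguous by-visit windows are optional. Added rows for Weeks 33, 41 and 49 would be sparse and filled mostly by patients whose treatment ended there.

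The cost is SAP wording and one extra table per lipid endpoint, with no new visits, samples or patients. The downside is small: exposure at EoT runs from about 24 weeks (Day 169) to 52 weeks (Day 365), and for patients whose EoT is Week 25 or 27 the value repeats the primary one.
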